10 PHARMAKOKINETICS AND EVALUATION OF RECOVERY

The incremental recovery of *Human-cl rhFVIII* can optionally be determined with the first *Human-cl rhFVIII* administration or within the first three months after treatment start with *Human-cl rhFVIII*. It is recommended to be controlled every 6 months.

Blood samples for the calculation of the incremental recovery will be taken before study drug injection and after 0.25 and 1 hour post-infusion.

FVIII:C values below the limit of quantification will be set to 0 for recovery calculations.

In-vivo incremental recovery will be calculated in the following way with both assays (chromogenic (CHR) and one-stage (OS) assay):

Recovery (according to assay a) (In vivo incremental recovery)	will be determined from the FVIII level before ($C_{pre,a}$) and the peak level after ($C_{max,a}$) the injection of Human-cl rhFVIII : $Re\ c_a = \frac{(C_{max,a} - C_{pr,a}) \cdot BW}{D_a}$ where BW stands for the body weight in kg and D_a is the dose according to the actual potency of the FVIII concentrate as described in ^[1] below
-----------------------------------------------------------------------	---------------------------------------------------------------------------------------------------------------------------------------------------------------------------------------------------------------------------------------------------------------------------------------------------------------------------------------------------------------------------------

^[1] The actual dose D_a based on the real potency of the batch of *Human-cl rhFVIII* used will be calculated as $D_a = D_{nom} * \frac{ActualPotency(a)}{LabeledPotency}$ where D_{nom} stands for the nominal Dose according to the product label and a stands for the respective assay: chromogenic assay or one-stage assay.

Summary statistics per time point will be prepared for the recovery, including mean and standard deviation, median, range, geometric mean and the associated geometric standard deviation and confidence intervals.

Intra-subject variability over different recovery measurements will be shown graphically in recovery profiles.

Plots showing mean ± standard deviation of the factor VIII concentrations per assay and per nominal time point will be presented.

In the course of ITI treatment, recovery will be determined after inhibitor elimination to test if the recovery is at least 66% of normal (defined as 1 IU FVIII/kg BW raises the plasma FVIII activity by 1.5%).

Half-life calculation for patients on ITI

Available PK data for half-life determination of *Human-cl rhFVIII* in patients on ITI will be calculated. In the course of ITI treatment it will be tested, if the half-life is at least 6 hours.

T _{max}	Time when C _{max} is observed	Timing starts at end of injection
T _{1/2}	Elimination half-life	using linear regression on the terminal phase* of the logarithm of the concentration; $T_{1/2} = \frac{\ln(2)}{K}$ (where K, the elimination rate constant, is determined as the slope of the regression line)

*The non-compartmental approach does not presume that the plasma concentration follows a mono-exponential decay during the complete elimination phase ($t \geq T_{max}$). The appropriate time point when the terminal elimination phase starts will be determined automatically by the Software WinNonlin using the algorithm described in APPENDIX I: DETERMINATION OF SLOPE OF ELIMINATION CURVE BY NON-COMPARTMENTAL PK ANALYSIS WITH WINNONLIN® [[2] , Chapter 9, pages 218-219]. In addition visual examinations on the choice of the software will be performed on individual plots of the natural logarithm of the plasma levels $\ln(C)$ (CHR and OS)

Half-lives and recovery determinations in ITI patients will be listed and used for the assessment of complete success of an ITI treatment.

10.1 Complete success of ITI therapy

Complete success of a patient’s ITI will be defined as:

- FVIII:C inhibitor negative (<0.6 BU) (at two sequential measurements)
- Recovery ≥ 0.99 %/(IU/kg BW) (= 66% of 1.5 % (IU/kg BW))
- terminal half-life ≥ 6 hours

Complete success is

- 1) documented in the “ITI Study Completion” by the investigator and
- 2) derived from the documented data on the objective criteria
 - in the inhibitor data
 - as derived from the recovery/half-life data
(central and/or local lab determinations with one-stage assay and/or chromogenic assay)

If more than one lab determination is available (e.g. local and central lab; several assays), worst available values are taken into account for the inhibitor criterion (highest titre) and the recovery criterion (lowest IVR); this also applies for the half-life criterion (lowest half-life). However, there may be exceptions when there is a difference in available data for PK analysis and one of the series of measurements is expected to provide more reliable estimations of the terminal half-life data than the other(s); if necessary, reliability of series of measurements in terms of available data for PK analysis will be assessed in data review meetings before interim and final analysis.

11 **EVALUATION OF SAFETY PARAMETERS**

11.1 **Adverse Events**

All adverse events occurring or worsening after initiation of study treatments until the completion visit (treatment emergent AEs) will be displayed in summary tables and listings.

Incidences of adverse events will be given as numbers and percentages of subjects; for AEs judged to be related to study drug or occurring during or within 24 hours of the end of an infusion also the numbers and percentages of infusions associated with such AEs will be presented:

- Any AE (by MedDRA (version 15.0 or later) preferred term (descending frequency) and by MedDRA System Organ Class (SOC))
- Any serious AE (by MedDRA System Organ Class (SOC)/ preferred term)
- Any AE probably or possibly related to the trial drug (by MedDRA System Organ Class (SOC)/ preferred term)
- Any AE temporally related (within 24 hours after end of infusion*) to the trial drug (by MedDRA preferred term (descending frequency) and by MedDRA System Organ Class (SOC))
- Any severe AE (by MedDRA System Organ Class (SOC)/ preferred term)
- Any withdrawal due to AE (Adverse drop-out)

* In case another infusion starts within the 24 hours the AE will be related to the last infusion.

Summary tables for AEs will be given by SOC and preferred term. Additionally, AEs will be summarized by severity and relationship to study treatment. These summary tables will feature total counts and counts, prior exposure days to *Human-cl rhFVIII* and total amount of *Human-cl rhFVIII* used prior to the AE to evaluate the need of further investigation of any apparent pattern or trend in AE rates.

The MedDRA coded terms and the corresponding original terms used by the investigator will be listed.

All adverse events for each subject will be listed in Appendix 16 of the CSR, featuring the following data:

- Subject identifier and characteristics (age, weight)
- The adverse event (preferred term, reported term)
- Onset, date of resolution and duration of the adverse event
- Severity (mild, moderate, severe)
- Seriousness (serious/non-serious)
- Action taken - General (none, drug therapy (other than IMP) started, tests performed, other (to be specified)) and on study drug (none, product withdrawn, dose reduced, dose increased)
- Outcome (recovered, recovering, not recovered, recovered with sequelae, fatal, unknown)
- Causality assessment (probable, possible, unlikely, not related)
- Study treatment at time of event or most recent study treatment taken, including dose and batch number
- Previous exposure to *Human-cl rhFVIII* (exposure days and total amount used)

11.2 Laboratory Data

Routine laboratory parameters will be listed for all subjects, using indicators for values outside the associated reference ranges. Laboratory parameters will be tabulated, and the sample characteristics will be presented by time point. In addition statistics on the changes from baseline (i.e. Screening for fixed times of schedule, and before surgery for surgeries) will be provided. A brief statement will be included in the CSR to highlight noticeably outliers or patterns.

All laboratory parameters will be listed with their associated units and normal reference ranges.

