After ED 20 has been reached and until 100 EDs, patients will visit the study site every 10-12 EDs. At these visits, patients' body weight will be checked, and blood samples will be obtained for FVIII inhibitor screen (after a wash-out period of at least 2, but preferably 3 days after the previous IMP administration). IMP injection is possible after blood sampling. The patient diary will be reviewed (any IMP injection, any bleed) in order to transfer data into the CRF. The occurrence of AEs and changes in concomitant medication will be checked and documented.

3-Monthly (± 2 weeks) Follow-Up Visits (calculated from Screening Visit):

If appropriate, the above described follow-up visits may be combined with the regular quarterly (every 3-months ( $\pm$  2 weeks)) Follow-Up visits, where some additional investigations will be performed: the safety laboratory parameters will be assessed and – in case IMP is injected after blood sampling – vital signs will be measured pre- and 30-60 minutes post-injection.

At these visits, patients' body weight will be checked, and blood samples will be obtained for FVIII inhibitor screen (after a wash-out period of at least 2, but preferably 3 days after the previous IMP administration). The patient diary will be reviewed (any IMP injection, any bleed) in order to transfer data into the CRF. The occurrence of AEs and changes in concomitant medication will be checked and documented. The Additional Health Economic Evaluation will be completed by the parents/legal guardians.

Once every 6 months a physical examination is performed.

If the optional *in vivo* recovery investigation is done, it is recommended with the first *Human-cl rhFVIII* administration, or within the first three months after treatment start with *Human-cl rhFVIII*, in any case in a non-bleeding patient. Controls approximately once every 6 months are recommended. Recovery visits should be timed so that they coincide with other study visits whenever possible. The *in vivo* recovery will be calculated from the

Name of Sponsor/Company: Octapharma AG, 8853 Lachen, Switzerland	
Name of Investigational Product:	Protocol Identification Code:
Human-cl rhFVIII	GENA-05
Name of Active Ingredient:	Date of Final Protocol:
Coagulation FVIII	01-Feb-2018

FVIII plasma levels before infusion and the peak level obtained from the 15 minutes and 1 hour post-infusion samples.

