# Follow-Up Visits (every 3 months $\pm$ 2 weeks):

If appropriate, the above-described follow-up visits may be combined with regular 3-monthly follow-up visits ( $\pm 2$  weeks), stipulating some supplementary investigations are performed: the safety laboratory parameters will be assessed (samples are analysed locally) and vital signs will be measured pre- and – in case IMP was injected – 30-60 minutes post-injection and the patient's BW will be measured.

Once every 6 months a physical examination is performed.

If the optional recovery investigation is done, it is recommended that it will be performed with the first *Human-cl rhFVIII* administration, or within the first three months after treatment start and every 6 months thereafter, in any case in a non-bleeding patient.

Recovery visits should be timed so that they coincide with other study visits whenever possible. The *in vivo* recovery will be calculated from the FVIII plasma levels before infusion and the peak level obtained from the 15 minutes and 1 hour post-infusion samples. Samples are analysed in the central laboratory.

In case the patient did not require any IMP from screening until the 3-Monthly Follow-Up visits during the first year, the blood sampling (inhibitor screen, safely laboratory) after 3 and 9 months is optional. After 6 and 12 months a sample is mandatory.

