11.3 Vital Signs

Blood pressure (systolic/diastolic), heart rate, respiratory rate and body temperature will be tabulated, and the sample characteristics will be presented by time point. In addition statistics on the changes from baseline (i.e. Screening for fixed times of schedule, and before surgery for surgeries) will be provided.

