14.3.1.21	T	Treatment-emergent adverse events by system organ class and preferred term – during and after surgical interventions (up to end of post-surgical treatment)	SAF, Safety-INF
14.3.2.1	T	Treatment-emergent serious adverse events by system organ class and preferred term	SAF, Safety-INF
14.3.2.2	L	Listing of Serious Adverse Events list of SAEs : full details including time since last Human-cl rhFVIII treatment, last Human-cl rhFVIII treatment (dose, batch),	SAF

		hospitalization?, treatment of AE, lab tests performed, relevant medical history, relevant concomitant medication reason for seriousness	
14.3.2.3	L	Listing of deaths	SAF
14.3.2.4	L	List of AEs leading to discontinuation of study medication or deaths	SAF
14.3.4.1	L	Abnormal laboratory value listing (2 sub-listings: hematology, clinical chemistry)	SAF
14.3.4.2.1-2	T	Safety Lab Panel summary statistics for each lab parameter and time point (excluding surgery) (2 sub-tables: Hematology, Clinical Chemistry)	SAF
14.3.4.2.3-4	T	Safety Lab Panel Change in lab parameter from baseline per time point (excluding surgery) (2 sub-tables: Hematology, Clinical Chemistry)	SAF
14.3.4.2.5-6	T	Safety Lab Panel summary statistics for each lab parameter before surgery, after surgery and change (2 sub-tables: Hematology, Clinical Chemistry)	SAF
14.3.4.3.1	T	Vital Signs Summary statistics on all vital sign determinations per time point (excluding surgery)	SAF
14.3.4.3.2	T	Vital Signs: Changes Summary statistics on changes in vital sign determinations compared to baseline per time point (excluding surgery)	SAF
14.3.4.3.3	T	Vital Signs Summary statistics on all vital sign determinations per time point before, during and after surgery	SAF
14.3.4.3.4	T	Vital Signs : Changes Summary statistics on changes in vital sign determinations during and after surgery compared to before surgery	SAF
14.3.4.3.5	T	Physical Examination shift tables on the evaluations of each category included in the physical examination (baseline vs. month 6 visit)	SAF
16.2		Listings provided as appendices to the CSR	
16.2.1.1	L	Prematurely discontinued subjects (inc. time in study, reason for premature discontinuation, age, total dose, total dose per kg and number of EDs)	All
16.2.1.2	L	Study completion 2 subtables for main and ITI study	All
16.2.2	L	Protocol violations flagged by “minor” and “major”	All

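### Scheduled laboratory and vital-sign changes use a Screening baseline and a Screening visit clock, so a child first dosed later adds untreated values to post-baseline rows

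*SAP*

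**What the plan says.** **Baseline.** For laboratory data, SAP 11.2 states: "In addition statistics on the changes from baseline (i.e. Screening for fixed times of schedule, and before surgery for surgeries) will be provided". SAP 11.3 repeats the rule for vital signs: "In addition statistics on the changes from baseline (i.e. Screening for fixed times of schedule". Protocol 9.2.4 also names screening as the laboratory baseline.

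**Tables.** The SAP Section 13 list describes Tables 14.3.4.2.3-4 as "Change in lab parameter from baseline per time point (excluding surgery") and the physical-examination shift, Table 14.3.4.3.5, as covering categories "included in the physical examination (baseline vs. month 6 visit"). All use the Safety population, which SAP 5.1 defines as everyone dosed at least once.

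**Visit clock.** The protocol outline heads the 3-monthly visits "Follow-Up Visits (calculated from Screening Visit"), and Protocol Table 3 agrees.

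**Late first dose.** Protocol Table 1 does not require an injection at Screening, and Protocol 5.4 recommends starting prophylaxis with the first bleed. Protocol 6.1.2 plans for a gap: "In case the patient did not require any IMP from screening until the 3-Monthly Follow-Up visits during the first year", it says, "the blood sampling (inhibitor screen, safely laboratory) after 3 and 9 months is optional". It then adds: "After 6 and 12 months a sample is mandatory". This waiver names blood sampling only.

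**The concern.** A row headed change from baseline at Month 6 combines children who have been treated for some time with children who have not yet had a dose. The planned N and n count patients in the population and patients contributing. They do not separate dosed from undosed, so a reader cannot tell how much exposure lies behind the row.

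Even for a child dosed before the visit, change from Screening includes his untreated time up to ED1.

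The SAP handles the distinction elsewhere. SAP 6.4.2 calculates age at both dates and interpolates body weight to ED1, and SAP 7 takes age at the first administration. Adverse events are restricted to those after treatment starts (SAP 11.1), and time to inhibitor runs from ED1 (SAP 3.4.1). Laboratory and vital-sign summaries have no such rule.

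At stake is how far secondary descriptive safety tables can be interpreted, including the short statement on laboratory outliers or patterns that SAP 11.2 plans for the study report.

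**Working it through.** The plan gives no figure on this point, so there is none to reproduce. The check has three parts.

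**1. Untreated rows per child, from the schedule.** Inputs are visits at Months 3, 6, 9 and 12 after Screening, with the blood-sampling waiver at Months 3 and 9 (Protocol 6.1.2 and Table 3). Vital signs are due at each 3-monthly visit; only the 30-60 minute reading depends on an injection (Protocol 7.3.4). A visit is untreated if it falls before ED1.

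| ED1 | Untreated visits | Laboratory, mandatory | Laboratory, optional | Vital signs |
|---|---|---|---|---|
| Month 5 | 3 | 0 | 1 | 1 |
| Month 7 | 3, 6 | 1 | 1 | 2 |
| After the Month 12 visit, before the Month 15 visit | 3, 6, 9, 12 | 2 | 2 | 4 |

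The last line holds only for a first dose before the Month 15 visit. A later ED1 adds further rows, since participation can last 5 years and the waiver covers only the first year. In the first and second lines, the Month 6 physical examination is after ED1 and before ED1 respectively. Children who are never dosed are outside the Safety population and add nothing.

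**2. Untreated share of one child's change.** For a visit at Month 12, share = (ED1 − baseline) / (12 − baseline), in months from Screening.

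- ED1 at Month 7, Screening baseline: 7/12 = 58%.
- ED1 at Month 7, baseline at the Month 6 sample: (7 − 6)/(12 − 6) = 1/6 = 17%.
- ED1 at Month 5, Screening baseline: 5/12 = 42%.
- ED1 at Month 5, baseline at the Month 3 sample: (5 − 3)/(12 − 3) = 2/9 = 22%. If the optional sample was not taken, the laboratory share stays at 42%.

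**3. Effect on a table mean (assumptions only).** Let u be the undosed share of the row, d the mean change in dosed children and g the mean change in undosed children. The row shows (1 − u)d + ug, so its error as a summary of dosed children is u(g − d). None of u, d or g is in the documents. With d = 10 in arbitrary units:

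| g | u = 10% | u = 30% | u = 50% |
|---|---|---|---|
| 0 | 9 | 7 | 5 |
| 5 | 9.5 | 8.5 | 7.5 |
| 10 | 10 | 10 | 10 |
| 15 | 10.5 | 11.5 | 12.5 |

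The table shows only that the error can have either sign, and that it vanishes when u = 0 or g = d. It does not estimate the effect in this trial. Protocol 4.1 expects mainly newborns and infants, so undosed values may also move with age, and g = 0 has no special claim.

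**The case against.** The strongest reply is that nothing here is mislabelled. The SAP states its baseline openly, the protocol names the same one for laboratory data, and no table in question is presented as on-treatment change or drug effect. The trial is uncontrolled and descriptive. Investigator-rated laboratory abnormalities are reported as adverse events (Protocol 7.3.3), and Protocol 7.3.1.2 does not count findings that existed before the first dose unless they worsen. Treatment-emergent ALT or AST rises above 3 times the upper limit are followed individually. Doses, laboratory values and vital signs are all listed, so dosing status can be recovered.

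Most of this stands. It rules out a charge that the SAP departs from the protocol, and it limits what is at stake to smaller shifts outside the adverse-event route. It does not remove the point. Recovery means matching dose and sampling dates by hand, and no planned summary shows the split. SAP 3.4.9 also lists vital signs and laboratory parameters beside adverse events as measures of safety.

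Two further limits apply. Readings taken after an injection cannot be untreated, so only the other vital-sign readings are affected. SAP 11.4 and the shift-table title do not say what baseline means for the physical examination. Screening is the natural reading, being the only scheduled examination before Month 6, but it is an inference.

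**Conclusion.** The point holds as a modest weakness, shared by protocol and SAP, in secondary descriptive safety tables. By the plan's own rules, a Safety-population child with ED1 after Month 6 contributes an untreated laboratory value at Month 6. With ED1 after Month 12 he contributes another at Month 12. Months 3 and 9 are possible additions. Untreated vital signs enter at every 3-monthly visit before ED1, post-injection readings excepted. The Month 6 physical-examination shift is likely affected, subject to the inferred baseline.

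The per-child counts rest on the visit schedule alone. The effect on any mean rests on an undosed share and on changes that the documents do not give; it may be zero.

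A reader might infer that these tables dilute or hide a toxicity signal. The documents do not support that: the direction is unknown, and clinically significant abnormalities have their own route. Nor does the point reach the inhibitor endpoint, the adverse-event tables or the efficacy analyses.

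**What to change.** In SAP 11.2 to 11.4:

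- Define baseline for laboratory data, vital signs and physical examination as the last value before the first dose (ED1).
- Exclude pre-ED1 results from the post-baseline rows of Tables 14.3.4.2.1-4, 14.3.4.3.1-2 and 14.3.4.3.5.
- Flag those results as pre-treatment in Listings 14.3.4.1, 16.2.8.1, 16.2.8.6 and 16.2.8.7.1. Listing 16.2.7.3 already separates adverse events in this way.
- Show the number of dosed children at each time point.
- Keep the Screening-based tables as supportive, for consistency with Protocol 9.2.4 and with the interim analysis.

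A summary by exposure days is optional. If added, it needs a class above 100 exposure days or a separate category for immune tolerance induction, because those children can pass 100.

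The cost is programming. Blood-sampling dates and times are recorded (Protocol 7.3.3), and every dose is in Listing 16.2.5.1. For vital signs and examinations, Protocol Table 3 places the pre-injection assessment before any dose given at that visit, so visit date and that position should suffice; this should be confirmed against the case report form.

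The downsides are smaller n in the early rows, no gain where Screening is the only value before ED1, and growth-related change that remains in any baseline comparison. Nothing changes for children dosed at Screening, and little for those dosed soon after it.

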11.3 Vital Signs

Blood pressure (systolic/diastolic), heart rate, respiratory rate and body temperature will be tabulated, and the sample characteristics will be presented by time point. In addition statistics on the changes from baseline (i.e. Screening for fixed times of schedule, and before surgery for surgeries) will be provided.

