## 1.3 Benefit-Risk Statement

On the basis of data available for adult and children (PTPs), the half-life and the recovery of *Human-cl rhFVIII* are similar to other already licensed rFVIII preparations. It can be concluded that *Human-cl rhFVIII* is efficacious in the prevention and in the treatment of BEs and during surgical prophylaxis in patients with inherited FVIII deficiency.

Comparable to other rFVIII preparations, the following adverse drug reactions (ADR) may occur by using *Human-cl rhFVIII*:

- 1. Allergic or anaphylactic types of reactions. Observed symptoms may include fever, chills, nausea, urticaria, pruritus, dizziness, chest tightness, shortness of breath, and very rarely anaphylactic shock.
- 2. Development of antibodies (inhibitors) against FVIII.

In conclusion, the hitherto existing clinical and pre-clinical data allow the conclusion that participating in this study does not represent any additional risk to the included patients in terms of immunogenicity and safety.

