## 3.2 Overall Study Design and Plan

This study is designed as a prospective, multicentre, multinational, open-label, non-controlled phase III study in 100 male PUPs (i.e. patients without any previous treatment with FVIII concentrates or other blood products containing FVIII) who are suffering from severe Haemophilia A (FVIII:C < 1%). Around 40 centres worldwide are planned to participate in this study.

For each patient, the exposure to *Human-cl rhFVIII*, the efficacy of *Human-cl rhFVIII* in the prevention and the treatment of bleeds, the frequency of break-through bleeds in case of prophylactic treatment, the efficacy in surgical prophylaxis, and the overall safety and tolerability of *Human-cl rhFVIII* will be thoroughly assessed. In the course of the follow-up visits (i.e. every 3-4 EDs until ED 20, then every 10-12 EDs until ED 100), scheduled to be performed after the Screening Visit, FVIII inhibitor levels will be assessed for each patient. If appropriate, these visits may be combined with the additional regular 3-monthly ( $\pm$  2 weeks) follow-up visits, stipulating some supplementary investigations are performed.

The occurrence of AEs and changes in concomitant medication will be checked and documented at each follow-up visit. A patient completes the study by reaching 100 EDs, or after a maximum study participation period of 5 years from screening. In patients who develop FVIII inhibitors and start ITI treatment, the maximum length of ITI will be 36 months. In patients undergoing surgical interventions, treatment details will be documented for the pre-, intra-, and post-operative phase, respectively.

The study is planned to start in the 4th quarter of 2012 and continues until the 4th quarter of 2018, except for those patients continuing Immune Tolerance Induction Therapy.

The tables below summarise the assessments to be performed at the individual visits:

Written informed consent for patients' parents / guardians	$\checkmark$
Inclusion/exclusion criteria check	$\checkmark$
Demographics, Medical History, risk factors	✓
FVIII gene mutation analysis*	✓
FVIII level	✓
FVIII inhibitor screen	✓
Safety lab tests	$\checkmark$
Physical examination	$\checkmark$
Vital signs	(baseline and 30-60 minutes post- treatment, in case IMP is injected)
Body weight and height	$\checkmark$
Immunogenotyping*† (HLA-typing, immune response gene profiling, FVIII ethnic haplotype determination)	✓
RNA expression analysis†¥	✓

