# 7.3.4 Vital Signs and Physical Examination

Vital signs (blood pressure, heart rate, respiratory rate, body temperature) will be assessed at the following time-points: at screening, prior and – in case IMP was injected – 30-60 minutes after the end of the injection at 3-monthly ( $\pm 2$  weeks) visits, and prior and – in case IMP was injected – 30-60 minutes after the end of the injection at the completion visit. During surgical procedures vital signs will be assessed before, during and at the first post-operative day.

A physical examination needs to be performed at screening, once every 6 months and at study completion.

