3.4.6 Actual and Labelled Potencies

For all batches of *Human-cl rhFVIII*, the actual potencies, i.e. the content of FVIII expressed as IU, are provided by the central laboratory; these data will be provided to the statistician in order to be available for the analysis. The actual potencies will be determined using both assay methods, CHR and OS, and used accordingly for calculations based on each assay. Should the central laboratory not provide one single potency determination per lot per assay, the potency for one lot with one assay will be calculated as the geometric mean of the values provided for the lot/ assay method.

Calculation of recovery for non-ITI patients will be based on the actual potency whereas dosing will be based on the labelled potency.

3.4.7 **Incremental Recovery**

Investigations of incremental recovery (optional) can be done with the first *Human-cl rhFVIII* administration (40 IU FVIII/kg BW, labelled potency), or within the first three months after treatment start with *Human-cl rhFVIII*, but in either case in a non-bleeding patient. They are recommended being controlled every 6 months thereafter. At these visits, blood samples for the calculation of the incremental recovery will be taken before study drug injection and 0.25, and 1 hours after end of injection.

3.4.8 **Other non-routine laboratory data**

The following non-routine laboratory data will be collected. However, the details on variables supplied by central laboratories are not yet known at the time point of creation of this version of the analysis plan:

- Immunogenotyping: F8 gene mutation analysis (mandatory), categorization in null/non-null and high/low risk mutation, HLA-typing, immune response gene profiling, F8 ethnic haplotype determination (optional), (EDTA blood)

The following data generated in the study will not be analysed under this SAP:

- RNA expression analysis (optional) (whole blood, RNase-free conditions)
- *In vitro* immunogenicity of FVIII products (optional) (citrate blood)

3.4.9 **Clinical Safety**

Clinical safety and tolerability will be assessed by monitoring vital signs, adverse events and laboratory parameters, including inhibitors against FVIII:

- Vital signs (blood pressure, heart rate, respiratory rate, body temperature) will be assessed at the following time-points:
 - at screening,
 - before and – in case IMP was injected – 30-60 minutes after the end of the infusion at the 3-monthly visits,

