11.4 Physical Examination

All abnormal findings from the physical examination will be listed. Shift tables will be prepared for the changes in assessments (normal/abnormal) of each body system over time.

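### Vital signs are collected in pre/post-injection pairs, but no within-visit change is planned; changes are taken from Screening and the only listed physical-examination shift table stops at month 6

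*SAP*

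**What the plan says.** **Collection of vital signs.** Protocol 7.3.4 asks for blood pressure, heart rate, respiratory rate and temperature before and, where IMP was injected, "30-60 minutes after the end of the injection at 3-monthly" visits, with the same rule at completion. SAP 3.4.9 repeats the scheme: "30-60 minutes after the end of the infusion at the 3-monthly visits". Table 1 of the protocol also foresees a post-treatment reading at Screening, "in case IMP is injected".

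**Analysis of vital signs.** SAP 11.3 tabulates values by time point and then defines change: "In addition statistics on the changes from baseline (i.e. Screening for fixed times of schedule, and before surgery for surgeries) will be provided". SAP section 13 implements this in four tables:
- 14.3.4.3.1: levels per time point
- 14.3.4.3.2: change from baseline per time point
- 14.3.4.3.3: levels around surgery
- 14.3.4.3.4: change from before surgery

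**Physical examination.** Protocol 7.3.4 schedules it at screening, every six months and at completion. SAP 11.4 states: "Shift tables will be prepared for the changes in assessments (normal/abnormal) of each body system over time". The only matching entry in SAP section 13 is Table 14.3.4.3.5: "shift tables on the evaluations of each category included in the physical examination (baseline vs. month 6 visit".

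**Timing.** The protocol counts the 3-monthly visits from Screening (synopsis and Table 3). Protocol 6.1.2 has a sampling rule that begins "In case the patient did not require any IMP from screening until the 3-Monthly Follow-Up visits during the first year"; it makes samples optional at months 3 and 9 and mandatory at months 6 and 12. The vital-sign and physical-examination tables use the safety population, which requires one dose at any time.

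**The concern.** A reading before an injection and another within the hour after it form a natural pair for detecting an acute effect. The first adverse drug reaction named in protocol 1.3 is "Allergic or anaphylactic types of reactions", with fever, chills and shortness of breath among the symptoms. Temperature and respiratory rate bear on these directly. The SAP accepts the principle of a nearby reference for surgery, but for injections at scheduled visits it refers everything back to Screening.

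Screening is a weak reference here for two reasons. First, protocol 4.1 expects mainly newborns and infants, followed for up to five years, so change from Screening mixes growth with any effect of treatment. Second, Screening and the early visits may all precede the first dose, so a change or shift can compare two untreated occasions.

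Safety and tolerability is a stated secondary objective. What is at stake is how much these descriptive tables can say about it.

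**Working it through.** The plan gives no figure to reproduce, so the check sets collection against analysis and then sizes the differences.

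**1. Collected against analysed, scheduled visits**

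| Item | Collected | Planned summary |
|---|---|---|
| Vital signs before injection | yes | level; change from Screening |
| Vital signs 30-60 minutes after | yes, if injected | level; change from Screening |
| Post minus pre, same visit | derivable | none |
| Physical examination at month 6 | yes | shift from baseline |
| Later six-monthly and completion examinations | yes | listings only |

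In 60 months there are up to 60/3 = 20 three-monthly visits at which a pair could arise, and no planned within-visit change table.

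**2. Precision against change from Screening.** With a common SD σ, the variance of a difference is 2σ²(1 − ρ). The variance of change from Screening divided by that of within-visit change is (1 − ρ_S)/(1 − ρ_V), where ρ_S is the correlation with Screening and ρ_V the within-visit correlation. The documents give neither. Assuming ρ_S = 0.2:
- ρ_V = 0.5: 0.8/0.5 = 1.6
- ρ_V = 0.9: 0.8/0.1 = 8

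The direction is clear as long as ρ_V exceeds ρ_S, but no single figure is supported.

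**3. Comparing the separate pre and post means.** If Table 14.3.4.3.1 shows pre and post as separate rows, a reader can subtract the means but can only treat them as independent. The standard error is then larger than the paired one by 1/√(1 − ρ_V): 1.41, 1.83 and 3.16 for assumed ρ_V of 0.5, 0.7 and 0.9.

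The pre mean also covers every patient at the visit, while the post mean covers only those injected. If a share f is injected, and their pre values differ by d SD from those of the others, the contrast is biased by (1 − f)d. For assumed f from 0.3 to 0.8 and d from 0.2 to 0.5, this runs from (1 − 0.8) × 0.2 = 0.04 SD to (1 − 0.3) × 0.5 = 0.35 SD.

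**4. Visits before ED1.** Take a child first dosed after month 6. Visits run from Screening, so months 3 and 6 are untreated. One later dose puts the child in the safety population, and no SAP rule removes visits before ED1. The month-3 and month-6 vital-sign changes and the month-6 examination shift then each compare two untreated occasions. The protocol allows for this case, but its frequency cannot be derived.

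**5. Physical-examination coverage.** Over the five-year maximum there are 60/6 = 10 six-monthly examinations after Screening, the last coinciding with completion. Table 14.3.4.3.5 uses 1 of these 10. Patients who reach 100 exposure days sooner have fewer. On every-other-day treatment, 100 exposure days take about 100 × 2 = 200 days from the first dose, so little beyond month 6 may be lost for a child dosed soon after Screening.

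**The case against.** A reader might infer that the planned outputs cannot show an infusion reaction. The documents do not support that. SAP 11.1 and Table 14.3.1.7 report adverse events starting within 24 hours of an infusion, by subject and by infusion, and protocol 9.2.4 includes clinically significant vital-sign abnormalities among the events displayed. SAP 3.4.9 names before and after injection as time points, so separate rows in Table 14.3.4.3.1 are the natural reading, although the SAP does not say so outright. Listing 16.2.8.6 gives the vital signs. A six-monthly examination is not meant to catch acute reactions; the weakness of its table is lost follow-up.

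It can also be said that:
- the surgery tables use a pre-surgery reference
- abnormal examination findings are listed without a month-6 limit
- the no-IMP rule is a contingency about blood sampling, not a forecast
- a child injected at the Screening visit may have a true pre-dose baseline there
- protocol 9.2.4 promises only tabulation of vital signs by time point, which the SAP already exceeds

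All of this stands and limits the point. It does not remove it. The adverse-event route depends on an investigator judging an abnormality significant, so a modest systematic shift would not appear there. The level summaries leave the contrast unpaired and with different denominators. Listings do not replace the shift tables that SAP 11.4 promises.

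**Conclusion.** The point holds as a minor weakness in secondary safety reporting, with three parts.

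1. At scheduled visits the pre/post pairs are collected, but no paired within-visit change is planned.
2. Change-from-Screening tables can include visits before ED1, in unknown number.
3. Table 14.3.4.3.5 does not deliver the over-time shifts of SAP 11.4. It may compare two untreated examinations, and it omits later six-monthly and completion examinations: at the extreme it uses 1 of 10.

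The first and third parts follow from the text alone. The second rests on the visit clock, the safety-population definition and the absence of a rule on visits before ED1. The gain in precision from pairing depends wholly on assumed correlations: a variance ratio of about 1.6 to 8 under the values above. A claim that pairing is worth some fixed multiple of patients would not be supported. The study is descriptive, and neither the primary inhibitor endpoint nor any efficacy result is affected.

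**What to change.** 1. **SAP 11.3 and section 13:** add a table of post-minus-pre change within visit for each vital sign, restricted to visits with an injection, with n per visit.
2. **Table 14.3.4.3.2:** define the vital-sign baseline as the last value before ED1, and exclude or flag visits before ED1. This also settles which Screening reading counts when IMP is injected at that visit.
3. **Table 14.3.4.3.5:** align it with SAP 11.4 by showing shifts from the last pre-ED1 examination to the worst post-ED1 examination and to the completion examination.

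The laboratory baseline can stay as it is, since protocol 9.2.4 sets it at screening. The cost is SAP wording and two or three added or redefined descriptive tables from data already collected. Nothing changes at the sites.
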